9.2 Setting

Approximately 200 postmenopausal women will be recruited in 25 UK centres. Patients will be greater than 18 years of age with ER+ locally advanced or metastatic breast cancer for whom a decision has been taken to initiate treatment with Afinitor (everolimus [RAD001]) in combination with exemestane.. There are no restrictions regarding the last anticancer treatment prior to enrolment. Participating patients may not take part in any clinical study in parallel to this, as this does not constitute routine medical practice and would thus be counter to the objectives of a NIS. Treatment may not be administered for the purpose of inclusion in the NIS, but must be given exclusively for the purpose of medical and therapeutic need.

9.2.1 Inclusion criteria

- Postmenopausal women with ER+ locally advanced or metastatic breast cancer;
- Aged >18 years of age;
- A decision has been taken to initiate Afinitor plus exemestane;
- Given written and signed informed consent to participate in the study.

9.2.2 Exclusion criteria

There are no exclusion criteria except the contraindications listed in the SmPC. Participating patients may not take part in any clinical study in parallel to this whilst on Afinitor plus exemestane, as this does not constitute routine medical practice and is, therefore, counter to the aims of an NIS. On progression, patients can be enrolled onto further clinical studies which will be captured in the eCRF until the end of the study.

9.3 Variables

9.3.1 Patient demographics and other baseline characteristics

In this non-interventional study, diagnostic measures and medically indicated examinations are documented only if they were conducted in accordance with normal routine practice. Prior to enrolment into this study, it is necessary to obtain the patient's written informed consent. Patients can be consented up to four weeks after treatment with Afinitor plus exemestane is initiated. The study aims to collect the following parameters at baseline where available:

- European Cooperative Oncology Group (ECOG) Performance Index if conducted
- General demography including age and gender;

- Medical history and current medical conditions;
- Concomitant medications;
- History and current disease status (including ER, PgR and Ki67 status if available, date of original diagnosis, date of first metastatic relapse if applicable and site involvement);
- Previous anticancer treatments for metastatic disease. The following information must be collected if available for all previous anticancer therapies: start date, end date, best response and reason for treatment discontinuation. Any history of stomatitis whilst on cancer therapy will also be collected if possible.
- Date of the prescription of Afinitor plus exemestane including dosage, reason for prescribing, date on which treatment will commence;
- Details of any planned prophylactic measures for stomatitis;
- EQ-5D questionnaire and subjective well-being assessment.

To determine eligibility at the screening visit, the following assessments may be performed and information captured:

- Physical examination and weight;
- Vital signs including blood pressure and heart rate;
- Safety laboratory assessments such as haematology, biochemistry, serum lipid profile, coagulation and urinalysis should be performed locally at the Investigator's discretion. Hepatitis screening will include: hepatitis B virus DNA, hepatitis B surface antigen, hepatitis B surface antibody, hepatitis B core antibody and hepatitis C virus ribonucleic acid polymerase chain reaction. If, at screening, laboratory results are out of range and clinically significant, these results should be captured on the medical history/current medical conditions eCRF;
- Tumour assessments at baseline may include clinical examination or radiographic or laboratory features, mirroring routine practice.

Thereafter, standard care would ideally be for patients to be contacted at 2 weeks, monthly then monthly to three monthly. The frequency of the visits will vary from patient to patient and due to clinician preference. Patients will be asked to complete the HrQoL and SWB questionnaires each time they attend the clinic. The HrQoL and SWB questionnaires will also be complete 30 days after trial end if possible as part of the end of trial visit.

9.3.2 **Primary outcome variable: stomatitis and non-infectious pneumonitis**

Instances of stomatitis and NIP will be assessed using the following variables:

- Incidence, severity, length of time to onset, duration and clinical course;
- Specific management of these events (including prophylaxis and interventions) will also be captured;

The expectation is that individuals participating in this study will be routinely questioned as to the presence of new or changed pulmonary symptoms consistent with lung toxicity. Computed Tomography scans and pulmonary function tests may be conducted, as clinically indicated, if there are symptoms that indicate that the patient has developed NIP. If NIP develops, the guidelines below should be followed. Table 9-2 provides dose modification instructions for stomatitis and NIP.

Table 9-2 Management of non-infectious pneumonitis and stomatitis

Adverse	Severity (Worst	Recommended	Management	Afinitor [®] Dose Adustment
Stomatitis	Grade 2 (symptomatic, but can eat and swallow modified diet)	Visual assessment	Symptomatic therapy only: mouthwashes, oral gels and sucralfate. Use water- based moisturizer to protect lips. Follow recommended oral care protocol.	Temporary dose reduction until recovery to ≤grade 1. Restart treatment at same dose. If stomatitis recurs at grade 2, interrupt dose until recovery to ≤grade 1. Restart treatment at 5mg daily.
	Grade 3 (symptomatic and unable to adequately eat or hydrate orally)	Visual assessment, including removal of dentures or partials	Symptomatic therapy only: mouthwashes, oral gels and sucralfate. Use water- based moisturizer to protect lips. Rinse mouth four times daily with a bland rinse such as salt and soda. Follow recommended oral care protocol	Temporary dose interruption until recovery to ≤grade 1. Restart treatment at 5mg daily.
	Grade 4 (symptoms associated with life- threatening consequences)	Visual assessment, including removal of dentures or partials	Symptomatic therapy only: mouthwashes, oral gels and sucralfate. Use water- based moisturizer to protect lips. Rinse mouth four times daily with a bland rinse such as salt and soda. Follow recommended oral care protocol. Consider systemic therapy.	Discontinue treatment.
Non-infectious pneumonitis	Grade 2 (symptomatic, not interfering with ADL)	CT scan with lung windows. Consider pulmonary function testing including: spirometry, DL _{CO} and room air O ₂ saturation at rest. Repeat at least every 12 weeks until return to within normal limits. Consider a bronchoscopy with biopsy and/or BAL.	Symptomatic therapy only. Consider corticosteroids if symptoms are troublesome.	Reduce study treatment dose by one dose level until recovery to ≤grade 1. Study treatment may also be interrupted if symptoms are troublesome. Patients will discontinue study treatment if they fail to recover to ≤grade 1 within three weeks.
	Grade 3 (symptomatic, interfering with ADL; O ₂ indicated)	CT scan with lung windows and pulmonary function testing including: spirometry, DL_{CO} and room air O_2 saturation at rest. Repeat at least every six weeks until return to within normal limits. Bronchoscopy with biopsy and/or BAL is recommended, if possible.	Consider corticosteroids if infective origin is ruled out. Taper as medically indicated.	Hold treatment until recovery to ≤grade 1. May restart study treatment within three weeks at reduced dose (by one level) if evidence of clinical benefit.
	Grade 4 (life- threatening; ventilator support indicated)	CT scan with lung windows ad required pulmonary function testing, if possible, including: spirometry, DL _{co} and room air O ₂ saturation at rest. Repeat at least every six weeks until return to within normal limits. Bronchoscopy with biopsy and/or BAL is recommended, if possible.	Consider corticosteroids if infective origin is ruled out. Taper as medically indicated.	Discontinue treatment.

Novartis	Confidential	Page 29
Non-interventional study protocol		Afinitor [®] : BOUDICA

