7.2.1 Stomatitis

Stomatitis is a very common adverse event of therapy with Afinitor and exemestane, often occurring soon after starting treatment and frequently regressing during the course of treatment [Porta 2011]. The frequency of all grade stomatitis and related events from the BOLERO-2 study was higher in the Afinitor and exemestane arm (67%) than in the control arm (12%). Grade 3 events occurred in 8% and <1% of patients, respectively but no grade 4 events were observed.

In the Afinitor and exemestane arm, more than one-third of all stomatitis events (grade \geq 2) were reported in the first two weeks (cumulative risk, 14%). The cumulative risks of stomatitis at six and 48 weeks were 26% and 37%, respectively, for Afinitor and exemestane versus 3% for exemestane and placebo (Figure 1 below).

Figure 1: Cumulative risk estimates for initial onset of grade 22 stomatitis [Rugo 2014]

Abbreviations: EVE, everolimus; EXE, exemestane; PBO, placebo.

Among 39 patients with grade \geq 3 stomatitis in the Afinitor plus exemestane arm, 97% experienced resolution to grade \leq 1 following dose interruption/reduction after a median of 3.1 weeks, and 82% had complete resolution after a median of 7.4 weeks. In the control arm, the median time to resolution from grade 3 to grade \leq 1 was 2.6 weeks (time to complete resolution was not assessable; one of two patients had complete resolution).

In the acute phase, various options are available to the physician to provide relief for the patient. The nature and duration of treatment depend on the degree of severity of the stomatitis and the specific criteria used by the individual physician. Since the data are as yet unclear, no definitive treatment recommendation for stomatitis with Afinitor can be provided. However, stomatitis occurring under treatment with mTOR inhibitors has been seen to differ in nature from the stomatitis that develops under certain chemotherapies. For this reason,

this NIS will record the measures used for prophylaxis and, if necessary, treatment of stomatitis and the outcome of these measures. The study will also attempt to identify predisposing risk factors.

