Metastatic sites involved at initiation of Afinitor and exemestane	х				
Prescription of Afinitor and exemestane	Х		Х	Х	Х
Current tumour treatment with Afinitor (dosage, dose reduction, pauses in treatment, reason for dose adjustment)		х	х	Х	Х
PFS				Х	Х
Patient Quality of Life questionnaires	X	X	X	X	X

Standard well-being questionnaire	Х	Х	х	Х	Х
Planned prophylactic measures and stomatitis treatment	Х	Х	Х	Х	
AEs/SAEs (including stomatitis and NIP)		Х	Х	Х	х
Reason for discontinuing treatment including sites of progression					х
Antineoplastic therapies since discontinuation of Afinitor plus exemestane					х

* Please note that this study allows up to 4 weeks to consent a patient on to the study.

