9.7 Data analysis

All analyses will be performed by Novartis or a contracted designee.

All the patients enrolled in the study will be analysed. The reference population for analysis will be patients who were enrolled and received follow-up, meeting eligibility criteria with at least one follow-up visit completed.

Each Investigator taking part in the study should enroll at least one patient and not more than 15 patients will be enrolled per centre. The enrolment period is one year, however this can be re-assessed depending on how recruitment is progressing. Data from all centres that participate in this protocol will be combined for analysis.

Descriptive statistics will be provided unless otherwise specified. These include n, mean, standard deviation, median and ranges for continuous, quantitative variables and frequencies and percentages for categorical, qualitative variables. For patients with screening assessments who do not enter the treatment period, data will only be listed. Further technical details and discussion of the following statistical considerations will appear in the statistical analysis plan, which will be finalised prior to database lock and the analysis.

For all analyses, baseline value will be defined as the latest assessment prior to first study drug administration.

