9.9 Limitations of the research methods

Being conducted solely in the UK means that the study results will only reflect the current status of clinical practice within the UK. Other countries will have different factors affecting their own clinical practice, such as re-imbursement issues and the availability of different competitor therapies.

10 **Protection of human subjects**

This clinical study was designed and will be implemented and reported in accordance with the International Conference on Harmonisation (ICH) Harmonised Tripartite Guidelines for Good Clinical Practice, with applicable local regulations, including the amended Medicines for Human Use (Clinical Trial) Regulations and the European Directive 2001/20/EC & 2005/28/EC, and with the ethical principles laid down in the Declaration of Helsinki.

It is unlikely that the study will place any study patients at risk as a result of their participation.

Compliance with Novartis and regulatory standards provides assurance that the rights, safety, and well-being of patients participating in NISs are protected (consistent with the principles that have their origin in the Declaration of Helsinki) and that the study data are credible and responsibly reported.

This study was designed and will be implemented and reported in accordance with the Guidelines for Good Pharmacoepidemiology Practices of the International Society for Pharmacoepidemiology [ISPE 2008] and the Strengthening the Reporting of Observational Studies in Epidemiology guidelines [VonElm 2008].

Regulatory and ethical compliance

The protocol and the proposed informed consent form must be reviewed and approved by a properly constituted Independent Ethics Committee (IEC) before study start. A signed and dated statement that the protocol and informed consent have been approved by the IEC must be given to Novartis before study initiation. Prior to study start, the Investigator is required to sign a protocol signature page confirming his or her agreement to conduct the study in accordance with these documents and all of the instructions and procedures found in this protocol. The Investigator is also required to give access to all relevant data and records to Novartis monitors, auditors, Novartis Clinical Quality Assurance representatives, designated agents of Novartis, IECs and regulatory authorities as necessary.

Informed consent procedures

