Eligible patients may only be included in the study after providing written (witnessed, where required by law or regulation), IEC-approved informed consent, or, if incapable of doing so,

after such consent has been provided by a legally acceptable representative of the patient. If a patient's representative gives consent, the patient should be informed about the study to the extent possible given his or her understanding. If the patient is capable of doing so, he or she should indicate assent by personally signing and dating the written informed consent document or a separate assent form. Informed consent must be obtained before any data are collected. The process of obtaining informed consent should be documented in the patient source documents. Patients can be consented up to four weeks after the initiation of Afinitor plus exemestane.

Novartis will provide to treating physicians or other involved medical professionals in a separate document a proposed informed consent form that complies with the Declaration of Helsinki and the appropriate regulatory requirements.

Amendments to the protocol

Protocol changes or additions can only be made in a written protocol amendment approved by Novartis and, if appropriate, the IEC. Only amendments required for patient safety may be implemented prior to IEC approval. However, the Investigator is expected to take any immediate action required for the safety of any patient included in this study, even if this action represents a deviation from the protocol, in which case, Novartis should be notified of this action and the IEC at the study site should be informed within 10 working days.

Discontinuation of the study

Novartis reserves the right to discontinue this study under the conditions specified in the clinical study agreement.

Publication of study protocol and results

Novartis assures that the key design elements of this protocol will be posted in a publicly accessible database such as www.clinicaltrials.gov. At study completion and finalisation of the study report, the results of this study will also be submitted for publication and/or posted in a publicly accessible database of clinical study results.

The terms applying to the scientific publication of the results and the authors participating in these publications and presentations will be defined by Novartis Pharma, which retains the copyright on all important publications, including translations into other languages.

Study documentation

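### Consent up to four weeks after first dose, with no duty to approach every starter, leaves stomatitis incidence and time to onset open to selection on early outcome

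*Protocol*

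**What the plan says.** The consent window appears in three places in the protocol. Section 9.3.1 says: "Patients can be consented up to four weeks after treatment with Afinitor plus exemestane is initiated". The note under the follow-up schedule in section 9.1 reads: "Please note that this study allows up to 4 weeks to consent a patient on to the study". The informed consent procedures in section 10 repeat it: "Patients can be consented up to four weeks after the initiation of Afinitor plus exemestane". The same paragraph of section 10 adds: "Informed consent must be obtained before any data are collected".

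Eligibility in section 9.2.1 rests on disease, age, signed consent and this criterion: "A decision has been taken to initiate Afinitor plus exemestane". No section asks sites to approach starters consecutively or to log those not approached.

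Sections 9.1 and 9.3.4.8 start the observation period at treatment initiation, not at consent. Section 9.3.2 makes incidence and time to onset of stomatitis and non-infectious pneumonitis (NIP) primary. Section 9.7 restricts the reference population to eligible patients with at least one completed follow-up visit.

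Section 7.2.1 gives the cumulative risk of grade 2 or higher stomatitis on the combination in BOLERO-2 as 14% at two weeks, 26% at six weeks and 37% at 48 weeks. Section 9.9 gives one limitation: "Being conducted solely in the UK means that the study results will only reflect the current status of clinical practice within the UK".

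**The concern.** The expected visits at about two weeks and one month both fall at or inside the consent window. By then a site can know whether a woman has had stomatitis or has stopped treatment, and it may still be deciding whether to approach her. Women who stopped early, or who died, may never be enrolled. Women returning often for mouth symptoms may be approached more readily. The first pattern makes incidence too low and onset too late. The second does the reverse.

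This concerns who is in the cohort, not which events are recorded once a woman is in it. A statistical analysis plan can change how risk sets are formed, but it cannot recover starters who were never approached. The precision in Table 9-4 covers sampling error only and would not show the problem.

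**Working it through.** **1. The plan's own figure.** Clopper-Pearson limits for 80/200 are 33.15% to 47.15%, which agrees with Table 9-4 (33.2%, 47.2%). All eight rows reproduce to one decimal, so the table is correct for what it covers. The same method at 74/200 (37%) gives 30.3% to 44.1%, that is 6.7 points below and 7.1 above.

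**2. How much stomatitis falls inside the window.** Inputs from section 7.2.1, grade 2 or higher: 14% at week 2, 26% at week 6, 37% at week 48.
- Week 4, linear between weeks 2 and 6: 0.14 + (0.26 − 0.14) × 2/4 = 20%. A constant hazard gives 20.2%.
- Share of 48-week events by week 2: 14/37 = 38%. By week 4: 20/37 = 54%.
- Mean risk already passed at consent, if late consents are spread evenly over four weeks (linear 0, 14, 20%): (7% × 2 + 17% × 2)/4 = 12%.

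**3. Selection model.** Let e be the risk before consent, r the entry rate of women with an early event relative to those without, and s the share of source patients approached late. Women approached by first dose enter at the same rate as late-approached women without an early event.

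Cohort incidence = [(1 − s) × 0.37 + s × (r·e + 0.37 − e)] / [(1 − s) + s × (r·e + 1 − e)]

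The protocol gives neither r nor s. Taking s = 0.5, and multiplying top and bottom by 2:

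| Late consents | r = 0.5 | r = 2 |
|---|---|---|
| Spread evenly, e = 0.12 | (0.37 + 0.31)/(1 + 0.94) = 35.1% | (0.37 + 0.49)/(1 + 1.12) = 40.6% |
| All at week 4, e = 0.20 | (0.37 + 0.27)/(1 + 0.90) = 33.7% | (0.37 + 0.57)/(1 + 1.20) = 42.7% |

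The shifts from 37% are −1.9 and +3.6 points in the first row, and −3.3 and +5.7 points in the second. Against the half-widths in step 1 that is about 28% and 51%, then 49% and 80%.

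**4. Time to onset.** In the second row, the share of events with onset by week 4 moves from the true 54% to (0.20 + 0.10)/0.64 = 47% or (0.20 + 0.40)/0.94 = 64%.

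**5. NIP.** Section 7.2.2 gives a grade 2 or higher risk of 5% by week 12. If linear, that is about 5% × 4/12 = 1.7% by week 4, so selection on early NIP can move little.

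**6. A related recording problem.** Section 9.3.4.6 counts adverse events from the start of drug. Section 11 counts them only after signed consent and sends conditions present at consent to Medical History. With no selection at all, half the cohort consented late and the section 11 rule applied, counted incidence would be 0.37 − 0.5 × 0.12 = 31%, or 0.37 − 0.5 × 0.20 = 27%. This is distinct from selection, but any analysis by consent timing depends on resolving it.

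**The case against.** The protocol permits late consent but does not make entry depend on outcome. A reader might infer that the estimates are biased as a matter of fact. The document does not support that: nothing in it shows that sites will select, and the direction is unknown. Nor can the point be extended to the primary outcome as a whole, since NIP has few early events.

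Several supporting arguments that might suggest themselves are weak:
- The enrolment limit ("not more than 15 patients will be enrolled per centre") might seem to invite choice among candidates. But 200 patients in 25 centres average 8, and the cap allows 25 × 15 = 375, so it will seldom bind.
- The inclusion criterion does not conflict with late consent, because a decision already taken remains taken. No criterion requires a woman to be on drug when she consents, and section 10 allows a representative to consent for a patient unable to do so.
- A reader might infer that a comparison with BOLERO-2 is undermined. Section 8 gives higher audit rates as background, but section 9.7.1 calls the analysis solely descriptive and plans no such comparison.
- The annex checklist points to pages 38-40 for selection bias. It is dated December 2014, before the October 2015 amendment entry on informed consent, so it is slight evidence of an oversight.

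The size is also easily overstated. Placing every late consent at week 4 gives the larger shifts; spreading consents evenly roughly halves them.

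Delayed entry has limits too. It sets aside real early events and cannot restore women who were never enrolled.

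These objections narrow the claim but do not remove it. The window, the missing consecutive-approach rule, the time origin at first dose and the early stomatitis risk are all in the protocol's own text.

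**Conclusion.** The concern holds as an exposure to bias, not as demonstrated bias. Following the plan as written, entry can depend on early stomatitis or early stopping, and section 9.9 does not say so.

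On the assumptions shown (true grade 2 or higher risk 37%, half of source patients approached late, relative entry rate 0.5 or 2), the estimate moves to about 35% or 41% with evenly spread consents, and to 34% or 43% with all late consents at week 4. Each of these lies inside the exact interval of 30.3% to 44.1%. The relative entry rates and late share are assumed, and the week-4 risk is interpolated from BOLERO-2. The time course is given for grade 2 or higher only, whereas section 9.5 cites all-grade incidences. The figures are therefore an illustration, not a forecast.

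The point merits a change because the entry rule is set in the protocol and the remedy is cheap.

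**What to change.** Keep the four-week window and make these changes:
- **Sections 9.2 and 9.3.1:** require sites to approach, consecutively, every woman starting Afinitor plus exemestane, including those who have already had a toxicity or stopped. Ask each site for an anonymous count of women who started, were approached and consented.
- **Section 9.7.1:** report stomatitis incidence and time to onset separately for patients consented on or before first dose and those consented later. Add a delayed-entry analysis, left-truncated at consent, as a sensitivity analysis. Pre-consent events drop out of it whatever their enrolment rate. It still assumes that, among women event-free at consent, entry is unrelated to later risk.
- **Sections 9.3.4.6 and 11:** reconcile the adverse event definitions so that, once a late-consented patient has consented, onset dates of stomatitis and NIP are recorded back to first dose.
- **Section 9.9:** state the residual selection.

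The cost is protocol wording, a small amount of site logging, and a wider interval for the early weeks in the group consented by first dose. Treatment and clinical management do not change.
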